1.2 Rationale

Consistent with the Food and Drug Administration (FDA) requirements for premarketing safety databases, the proposed population in this clinical study is sufficiently diverse to adequately represent the target population (patients with moderate to severe acute pain for which parenteral opioid therapy is warranted) ([Food and Drug Administration, 2005](#)).

Consistent with the known pharmacological properties of oliceridine and clinical observations obtained from completed studies with oliceridine, essentially, only patients with contraindications to opioid therapy or other clinical considerations confounding an interpretation of safety, tolerability, or efficacy data have been excluded. Eligibility criteria therefore support evaluation of oliceridine in patients with a range of conditions warranting parenteral opioid therapy, treated across a clinical trial environment characterized by diverse site topologies (institutions, investigators) within the United States, for variable durations of treatment.

Oliceridine will be administered as-needed (PRN) via the IV route. Depending on the clinical considerations for which parenteral opioid therapy is warranted (eg, anticipated duration of therapy, clinical setting), a patient could receive oliceridine using clinician-administered bolus dosing, PCA, or both bolus and PCA.

1.3 Study Endpoints

1.3.1 Safety and Tolerability Endpoints

The safety and tolerability of oliceridine will be measured as the incidence of self-reported or observed AEs, including those related to vital sign measurements, oxygen saturation measurements, somnolence/sedation scores, physical examination findings, and clinical laboratory assessments. Somnolence/sedation will be measured using the Moline-Roberts Pharmacologic Sedation Scale (MRPSS; see Section 9.1) ([Moline, 2012](#)). The MRPSS is designed to provide a consistent method of assessing pharmacologic sedation and assist in the decision-making process regarding the administration of opioids, sedatives, and other agents which produce sedation. For patients receiving a parenteral opioid in current practice, intensive monitoring is the standard of care. This monitoring will be used in the current study to evaluate

Trevena, Inc.

Protocol CP130-3003

Version 5.0

14 Sep 2016

oliceridine. Protocol-specified patient monitoring is compatible with the Joint Commission Sentinel Event Alert for the safe use of opioids in hospitals ([The Joint Commission, 2012](#)).

1.3.2 Efficacy Endpoints

The analgesic efficacy of oliceridine will be measured using a 0-10 point numeric pain rating scale (NPRS, see Section 9.2). NPRS was selected given its frequent use in clinical practice and clinical research ([McCaffery, 1989](#)). The NPRS may be explained or shown to the patient, who responds by indicating a number ([Hjermstad, 2011](#)).

1.4 Risks and Benefits for Patients

The potential benefit of study participation is that patients may experience a reduction in pain as a result of treatment with oliceridine. Patients will also contribute to the clinical data set for oliceridine, an investigational product (IP). No other benefits of participation are anticipated.

The potential risks of study participation include lack of analgesic efficacy, known or unknown serious or non-serious AEs, and unknown risks inherent in the evaluation of an IP. Additional risks are those associated with medical evaluation, such as those associated with venipuncture.

Oliceridine preclinical and clinical data are summarized in the current IB. Investigators must become familiar with all sections of the IB before the start of the study.

Trevena, Inc.

Protocol CP130-3003

Version 5.0

14 Sep 2016

2 STUDY OBJECTIVES

2.1 Primary Objective

The primary objective is to evaluate the safety and tolerability of oliceridine in patients with moderate to severe acute pain for which parenteral opioid therapy is warranted.

2.2 Secondary Objective

The secondary objective is to evaluate the analgesic efficacy of oliceridine.

3 INVESTIGATIONAL PLAN

3.1 Overall Study Design and Plan

[figure not shown]
This phase 3, open-label, safety study will be conducted in inpatient hospitals, outpatient hospital departments, ambulatory surgical care centers, and emergency departments (EDs). Patients recruited in EDs may continue oliceridine treatment if hospitalized and parenteral opioid therapy is warranted.

Representative surgeries include orthopedic (eg, total hip replacement, total knee replacement, spine), abdominal (eg, upper or lower abdominal, perineal), gynecologic (eg, total abdominal hysterectomy), vascular, soft tissue, and surgical procedural pain.

Representative medical conditions include acute pancreatitis, acute exacerbation of existing noncancerous chronic pain, musculoskeletal pain, sickle-cell disease, inflammatory orofacial muscle pain, and renal colic. Medical conditions that could confound the evaluation of oliceridine are excluded, such as acute pain without a specific etiology, undifferentiated acute abdominal pain, acute breakthrough pain in palliative “end of life” care, and pain associated with advanced cancer (somatic, visceral, or neuropathic) or with concurrent use of chemotherapeutic or biologic agents for the treatment of cancer.

Representative ED conditions include visceral pain (eg, renal colic, upper abdominal pain, abdominal pelvic pain); nonvisceral pain (eg, traumatic and atraumatic acute musculoskeletal pain, chest wall pain, burns, orofacial pain/headache, cutaneous and soft tissue pain); procedural analgesia (eg, reduction of orthopedic fractures and dislocations, abscess incision and drainage); acute painful episodes associated with a medical condition (eg, sickle cell painful vaso-occlusive episode). Oliceridine will not be used to intentionally suppress a patient’s level of consciousness (procedural sedation and analgesia as defined by the American College of Emergency Physicians [ACEP]).

The study has four phases: a screening/baseline phase, a treatment phase (consisting of a predose period and a dosing period), an end-of-treatment phase, and a follow-up phase.

Figure 1: Study Schematic

Abbreviations: T_0 = time of first dose of oliceridine; h = hours

* Combined if occurring within 48 hours of each other, unless the clinical condition of the patient has significantly changed since screening

3.1.1 Screening/baseline phase

Written informed consent will be obtained before any protocol-related activities are conducted. All screening procedures will be completed within 14 days before the first oliceridine dose. Select standard of care assessments (eg, chemistry, hematology, urine or serum pregnancy test, urine or serum toxicology screen, electrocardiogram (ECG)) obtained before informed consent may be used as study data if protocol specifications and timeframes are met (see Section 3.6.1).

When screening and baseline procedures are anticipated to occur within 48 hours of each other, they may be executed as a single procedure, unless the clinical condition of the patient has significantly changed since screening.

Adverse events (AEs) occurring from time of informed consent to the follow up phase will be recorded in source and will also be recorded in eCRF if the patient receives oliceridine. Serious Adverse Events (SAEs) occurring from time of informed consent to the follow-up phase or 7 days after the last dose of oliceridine (whichever occurs later) will be recorded in source and eCRF; ongoing SAEs after this time frame will be followed until the investigator, medical monitor, and sponsor agree that the SAE is satisfactorily resolved. SAEs considered by the investigator to be related to oliceridine, regardless of the time of onset after treatment, should be reported.

Prior medications taken or administered within the 14 days before the first dose of oliceridine will be recorded in source and will also be recorded in eCRF.

3.1.2 Treatment phase

The treatment phase begins with the predose period and ends when the investigator documents that the last dose of oliceridine was administered and that the patient will no longer be treated with oliceridine.

The duration of treatment for each patient will be determined by the clinical need for parenteral opioid therapy. In current practice, parenteral opioids are used as-needed for up to several days.

Trevena, Inc.

Protocol CP130-3003

Version 5.0

14 Sep 2016

Although preclinical toxicology studies support intravenous (IV) administration of oliceridine for up to 14 days, it is unlikely that patients will receive oliceridine for that duration in the context of this study.

3.1.3 Predose period

Before dosing with oliceridine, vital signs (blood pressure, heart rate, respiratory rate), oxygen saturation, and somnolence/sedation will be measured. Somnolence/sedation will be measured using the MRPSS. During the predose period, an additional, post-surgical ECG will be performed only in surgical patients. Prior medications and AEs/SAEs will be recorded.

Pain intensity will be measured using a 0-10 point numeric pain rating scale (NPRS).

Predose period procedures will occur within 30 minutes before the first oliceridine dose. If the dosing period is delayed, predose period procedures (except the additional, post-surgical ECG performed only in surgical patients) will be repeated.

3.1.4 Dosing period

Oliceridine IV infusion may be administered either by clinician-administered bolus, PCA, or both bolus and PCA, according to the clinical situation.

During dosing with oliceridine, vital signs, oxygen saturation, and somnolence/sedation will be measured at any and all times during the dosing period consistent with individual patient need and institutional standards of care for a patient receiving a parenteral opioid. An ECG will be obtained 60 minutes after the first dose of oliceridine, and at every 24 hours of oliceridine treatment. Blood will be collected for oliceridine pharmacokinetics and future cytochrome P450 2D6 (CYP2D6) genotyping. Concomitant medications and AEs/SAEs will be recorded.

NPRS assessments will also be completed at 30 minutes +/- 10 minutes after the first dose of oliceridine and at any and all times during the dosing period consistent with individual patient need and institutional standards of care for a patient receiving a parenteral opioid.

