2. When the investigator documents that the last dose of oliceridine was administered and that the patient will no longer be treated with oliceridine, the treatment phase is complete and the end-of-treatment phase begins. A physical examination will be performed at this time.
3. Follow-up contact may be conducted in person or by telephone.
4. Procedures will be performed at any and all times during the dosing period consistent with individual patient need and institutional standards of care for a patient receiving a parenteral opioid.
5. Written informed consent.
6. If a surgical or medical patient. Refer to Section 9.3 for the ASA scale.
7. If an ED patient. Refer to Section 9.4 for the ESI scale.
8. Blood chemistry and hematology will be obtained using local laboratories and local laboratory range values.
9. Female patients of childbearing potential only.
10. If an ED patient.
11. Height may be obtained by measurement or patient attestation.
12. During the predose period, an additional, post-surgical ECG will be performed only in surgical patients.
13. ECG will be obtained during the Treatment Phase at 60 minutes after the first dose of oliceridine, and at every 24 hours of oliceridine treatment.
14. PK samples will be collected at two times during the treatment phase: sample 1 at 30 minutes (+/- 10 minutes) after the first dose; sample 2 between 1 and 2 hours after the first dose. Unscheduled PK samples may be required. Refer to Sections 3.5.2.3 and 3.6.3.
15. PCA patient training is required before PCA use. If PCA is planned, training will occur during the screening and baseline phases; if PCA is started during the treatment phase, training will occur before PCA use. Training is repeated according to patient need.
16. NPRS will be measured during the predose period, at 30 minutes +/-10 minutes after the first dose of oliceridine, and at any and all times during the dosing period consistent with individual patient need and institutional standards of care for a patient receiving a parenteral opioid (see Section 9.2).
17. Blood pressure, heart rate, respiratory rate, and temperature. Temperature will be measured at screening and baseline only.
18. Refer to Section 9.1 for the MPRSS.
19. Refer to Section 9.5 for the SOWS. If the patient is discharged or transferred before the time when the SOWS is to be performed, it will be performed one day after completion of the treatment phase and returned to the site by mail or in person.

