4.3.2 Individual Patient Stopping Criteria

Oliceridine is a μ -opioid receptor agonist; therefore, effects on BP and respiration should be anticipated.

As with conventional opioids, oliceridine will be administered PRN; for a patient, analgesia must be balanced with intolerability. In a situation of significant intolerability, temporary or permanent discontinuation may be warranted:

- Asymptomatic decreased BP, increased HR, or decreased or increased RR may require only temporary discontinuation without additional intervention.
- Symptomatic hypotension, tachycardia, advancing somnolence/sedation, or respiratory signs (bradypnea, tachypnea, decreased respiratory effort, and/or decreased oxygen saturation) require temporary discontinuation and may require additional intervention.
- Symptomatic hypotension, tachycardia, advancing somnolence/sedation, or respiratory signs (bradypnea, tachypnea, decreased respiratory effort, and/or decreased oxygen saturation) requiring urgent intervention also requires permanent discontinuation.
- Possibly or probably related increase in QTcF to ≥ 500 milliseconds, or increase in QTcF of > 60 milliseconds versus most recent pre-exposure QTcF requires: permanent discontinuation; urgent clinical laboratory assessment and correction of electrolyte abnormalities (eg, hypocalcemia, hypokalemia, hypomagnesemia); and hourly ECG until QTcF < 500 milliseconds.

Additionally, if a patient receives 60 mg of oliceridine within the first 12 hours, the patient will early discontinue oliceridine and will be managed conventionally. The assigned reason for early discontinuation will be “other” and with the comment “dosing limit” (see [Section 3.5.2.3](#)).

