4.2 Method of Assignment of Patients to Cumulative Dose Groups

This is an open-label study therefore the method of assigning patients to dose groups will be based on the actual dose received by the patient.

Depending on the clinical considerations for which parenteral opioid therapy is warranted (e.g., anticipated duration of therapy, clinical site/setting), a patient could receive oliceridine using clinician-administered bolus dosing or PCA dosing. For clinician-administered bolus dosing, the oliceridine initial dose is 1 mg to 2 mg. If clinically indicated, a 1 mg supplemental dose may be administered as early as 15 minutes after the initial dose. Subsequent doses are 1 to 3 mg every 1 to 3 hours PRN based on individual patient need and previous response to oliceridine. In settings where rapid analgesia is targeted (e.g., ED or post-anesthesia care unit (PACU)), the oliceridine initial dose is 1 mg to 3 mg. If clinically indicated, 1 mg to 3 mg supplemental doses may be administered every 5 minutes PRN. Subsequent doses are 1 to 3 mg every 1 to 3 hours PRN based on individual patient need and previous response to oliceridine. For PCA dosing, the oliceridine regimen will consist of a loading dose, a demand dose, and a lockout interval without a continuous baseline infusion.

Oliceridine PCA regimen:

- Loading dose: 1.5 mg.
- Demand dose: 0.5 mg.
- Lockout interval: 6 minutes.

If clinically indicated, throughout the treatment phase, a 1 mg supplemental dose may be administered PRN, taking into account the patient's utilization of PCA demand doses, individual patient need and previous response to oliceridine.

For purposes of analysis the cumulative dose groups will be grouped in the following categories where cumulative dose group will be defined as the sum of all individual doses:

Statistical Analysis Plan

Client: Trevena, Inc.
Version #: 1.0
Version Date: 20Dec2016

Protocol/CIP #: CP130-3003

Oliceridine <= 4 mg	Oliceridine >4 to 8 mg	Oliceridine >8 to 16 mg	Oliceridine >16 to 36 mg	Oliceridine > 36 mg	All Treated Patients
------------------------	---------------------------	----------------------------	-----------------------------	------------------------	-------------------------

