8.6 Analysis of Safety

The Safety Analysis Set will be used for all safety summaries. Summaries will be tabulated by cumulative dose group and for all groups combined.

Client: Trevena, Inc.
 Version #: 1.0
 Version Date: 20Dec2016

Protocol/CIP #: CP130-3003

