Missing		xxx	xxx	xxx	xxx	xxx	xxx		
n	Change	xxx	xxx	xxx	xxx	xxx	xxx		
Mean (SD)		xx.x (x.xx)	xx.x (x.xx)	xx.x (x.xx)	xx.x (x.xx)	xx.x (x.xx)	xx.x (x.xx)		
Median		xx.x	xx.x	xx.x	xx.x	xx.x	xx.x		
Min, Max		xx, xx	xx, xx	xx, xx	xx, xx	xx, xx	xx, xx		
Missing		xxx	xxx	xxx	xxx	xxx	xxx		
. . .									

Note: Percentages are based on the number of patients in each cumulative dose group.

Trevena, Inc.
Protocol CP130-3003

CONFIDENTIAL
Page x of y

- [a] See section 6.2.3 of the SAP for windowed time point intervals.
- [b] Baseline is the last non-missing value prior to the patient receiving the first dose of oliceridine.
- [c] Only patients with both a baseline value and a windowed time point value are summarized at a given windowed time point.

Programmer's Note: Repeat Parameter (unit) in each page if it wraps on to multiple pages.

Table 14.3.7.1.1
Selected QTcF Thresholds
(Safety Analysis Set)

Windowed Time Point [a]	Oliceridine <= 4 mg N=XXX n (%)	Oliceridine >4 to 8 mg N=XXX n (%)	Oliceridine >8 to 16 mg N=XXX n (%)	Oliceridine >16 to 36 mg N=XXX n (%)	Oliceridine >36 mg N=XXX n (%)	All Treated Patients N=XXX n (%)
Overall	xxx	xxx	xxx	xxx	xxx	xxx
Change from Baseline of > 30 msec	xxx (xxx.x)	xxx (xxx.x)	xxx (xxx.x)	xxx (xxx.x)	xxx (xxx.x)	xxx (xxx.x)
Change from Baseline of > 60 msec	xxx (xxx.x)	xxx (xxx.x)	xxx (xxx.x)	xxx (xxx.x)	xxx (xxx.x)	xxx (xxx.x)
Increase to > 500 msec	xxx (xxx.x)	xxx (xxx.x)	xxx (xxx.x)	xxx (xxx.x)	xxx (xxx.x)	xxx (xxx.x)
<T30 Minutes>	xxx	xxx	xxx	xxx	xxx	xxx
Change from Baseline of > 30 msec	xxx (xxx.x)	xxx (xxx.x)	xxx (xxx.x)	xxx (xxx.x)	xxx (xxx.x)	xxx (xxx.x)
Change from Baseline of > 60 msec	xxx (xxx.x)	xxx (xxx.x)	xxx (xxx.x)	xxx (xxx.x)	xxx (xxx.x)	xxx (xxx.x)
Increase to > 500 msec	xxx (xxx.x)	xxx (xxx.x)	xxx (xxx.x)	xxx (xxx.x)	xxx (xxx.x)	xxx (xxx.x)
...						

Note: Percentages are based on the number of patients in each cumulative dose group.

Baseline is the last non-missing value prior to the patient receiving the first dose of oliceridine.

[a] See section 6.2.3 of the SAP for windowed time point intervals.

Programmer's Note: Display all ECG windowed time points after overall.

Table 14.3.7.1.2
Summary of Electrocardiogram (ECG) Findings
(Safety Analysis Set)

Windowed Time Point [a] Finding	Oliceridine <= 4 mg N=XXX n (%)	Oliceridine >4 to 8 mg N=XXX n (%)	Oliceridine >8 to 16 mg N=XXX n (%)	Oliceridine >16 to 36 mg N=XXX n (%)	Oliceridine >36 mg N=XXX n (%)	All Treated Patients N=XXX n (%)

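### Patients treated for under 24 h have one scheduled on-drug ECG, at 60 minutes, yet their QTcF is tabulated under final total dose

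*Protocol*

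**What the plan says.** Protocol 3.1.4 sets the on-treatment ECGs: "An ECG will be obtained 60 minutes after the first dose of oliceridine, and at every 24 hours of oliceridine treatment". The Schedule of Events (Protocol 3.6, Table 2) repeats this in a footnote and has no ECG entry in the end-of-treatment or follow-up columns. Protocol 3.1.5 names none either. Other ECGs are possible: the note to the dosing column says "Procedures will be performed at any and all times during the dosing period consistent with individual patient need and institutional standards of care", and Protocol 4.3.2 requires "hourly ECG until QTcF < 500 milliseconds" once a QTcF stopping criterion has been met.

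SAP 4.2 forms five dose groups (up to 4, >4 to 8, >8 to 16, >16 to 36, and >36 mg). It says that "the method of assigning patients to dose groups will be based on the actual dose received by the patient" and that "cumulative dose group will be defined as the sum of all individual doses", that is, the final total. SAP 8.6 applies the groups to all safety results: "Summaries will be tabulated by cumulative dose group and for all groups combined". Three mock tables follow this layout, with an added column for all treated patients: 14.3.7.1 (ECG change from baseline), 14.3.7.1.1 ("Selected QTcF Thresholds") and 14.3.7.1.2 (ECG findings). Table 14.3.7.1.1 opens with 'Overall' rows, and Table 14.3.7.1.2 opens with a count of patients having any clinically significant ECG. Rows by time window come after. The footnotes of both tables base percentages on all patients in the dose group. Neither document relates an ECG to the dose received before it.

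**The concern.** A column headed by a dose range will be read as showing QTcF at that dose. An ECG at 60 minutes can reflect only what has been given by then. If most of the drug comes later and treatment stops before 24 h, no scheduled ECG follows the later doses, and the early value is filed under the total. A dose-related QTcF effect could then look weaker than it is, or flat across columns.

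Safety is the primary objective. QTcF is an exclusion criterion (Protocol 3.3.2), a stopping criterion (4.3.2) and a prespecified categorical outcome (SAP 6.3.5). The two upper columns are where a reader will look for a dose relation.

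**Working it through.** The documents state no figure for dose at the time of the ECG, so there is none to reproduce. The check applies the dosing rules in Protocol 3.5.2.2 to the ECG times.

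**1. Dose allowed by 60 minutes, one method at a time**

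- PCA (loading 1.5 mg, demand 0.5 mg, lockout 6 min): demands at 6, 12, ..., 54 min give 1.5 + 9 × 0.5 = 6.0 mg. A demand at exactly 60 min makes 6.5 mg. One 1 mg supplement (an assumption; no number limit is stated) gives 7.0 to 7.5 mg.
- Standard bolus: 2 + 1 = 3 mg, or 6 mg if a 3 mg subsequent dose falls at 1 h.
- Rapid-analgesia bolus: 3 mg at 0 min plus 11 supplements of 3 mg at 5, 10, ..., 55 min gives 3 + 11 × 3 = 36 mg, or 39 mg with one more at 60 min.

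**2. Earliest time the upper columns can be entered**

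- PCA: 1.5 + 0.5n > 16 first holds at n = 30, and 30 × 6 min = 3.0 h. 1.5 + 0.5n > 36 first holds at n = 70, and 70 × 6 min = 7.0 h.
- Standard bolus, 3 mg each hour after the first 3 mg: 3 + 3h > 16 first holds at h = 5; 3 + 3h > 36 first holds at h = 12.

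Both columns can therefore be reached well inside 24 h.

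**3. Dose allowed by 60 minutes as a share of each column's lower bound**

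| Method | Allowed by 60 min | Of 16 mg | Of 36 mg |
|---|---|---|---|
| PCA | 6.5 mg | 41% | 18% |
| PCA, one supplement | 7.5 mg | 47% | 21% |
| Standard bolus | 3 mg | 19% | 8% |
| Standard bolus, 3 mg at 1 h | 6 mg | 38% | 17% |

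A patient's total exceeds the lower bound, so the true shares are smaller.

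**4. How plausible this is at average use.** Protocol 1.1 gives mean phase 2 PCA use of 14.8 mg over 24 h with a 0.35 mg demand dose. At that rate 16 mg takes 24 × 16/14.8 = 26 h and 36 mg takes 58 h. If use scales with the demand dose (an assumption), 14.8 × 0.5/0.35 = 21.1 mg per 24 h, and the times are 18 h and 41 h. On the scaled rate, an average user can enter the >16 to 36 mg column with only the 60-minute ECG. An average user in the >36 mg column would also have the 24-hour ECG.

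**5. What each kind of row shows**

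- *T60-minute row.* PCA-only and standard-bolus-only patients have had about 1 to 7.5 mg by 60 minutes (at most one PCA supplement), whichever column they end in. The row cannot speak to the effect of the final dose for them, including those treated beyond 24 h. The SAP window runs to just under 1.5 h, by when PCA without supplements allows 1.5 + 14 × 0.5 = 8.5 mg.
- *Pooled rows.* Timing is lost. Suppose a column holds N patients, m of them have any ECG after the 60-minute one, and a proportion p of those m show a late event. The late contribution is then reported as p × m/N, because the other N − m count as non-events.
- *Unlabelled counts.* The mock threshold table prints a count beside 'Overall' and beside each window. It may be the number with an ECG, but the footnote still makes the whole dose group the denominator.

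**The case against.** The strongest reply is that much of this is already visible. Continuous ECG summaries are by time point (SAP 8.6.7), the other two tables have window rows, and the column for all treated patients does not depend on dose grouping. Table 14.3.7.1 summarises change only in patients with a value in that window. The findings table has a 'Missing' line in each window. Listings 16.2.3.1 and 16.2.8 give the times of doses and ECGs. This stands, and it confines the loss of timing to the pooled rows. But window rows show time rather than dose, and they do not change the percentage denominator.

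A reader might infer that the high-dose columns contain only QTcF taken after a few milligrams. The documents do not support that. The rapid-analgesia rule, which covers the ED and PACU, allows 36 mg by 55 minutes. PCA supplements have no number limit, and one patient may receive both bolus and PCA. Patients treated for 24 h or longer contribute later ECGs. Unscheduled ECGs are allowed, and the SAP's window from 1.5 to under 12 h has a place for them.

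Protocol 3.6.3 also plans model-predicted individual exposure, but neither document links it to QTcF.

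Finally, the study is descriptive and no formal ECG test is planned. That lowers the stakes without removing the misattribution, because the tables are the product.

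**Conclusion.** The point holds as a defect of attribution. For a patient treated for under 24 h, the only scheduled on-drug QTcF comes at 60 minutes and is reported under the final total. On PCA alone or standard bolus alone it follows at most 7.5 mg (allowing one PCA supplement), less than half of the >16 mg bound and about a fifth of the >36 mg bound. The defect is greatest in the pooled rows of Tables 14.3.7.1.1 and 14.3.7.1.2.

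Its extent cannot be computed, since the number of high-dose patients treated for under 24 h is not stated. On phase 2 use, with the scaling assumption, it is more plausible for the >16 to 36 mg column than for >36 mg. Nor do the documents show that a QTcF effect exists and would be hidden. They show only that these tables could not separate low dose at the ECG from no effect at high dose. The change is cheap and bears on the primary objective, so it should be made.

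**What to change.** In SAP 8.6.7:

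1. Add a tabulation of QTcF change and QTcF thresholds by cumulative dose received up to the date and time of each post-dose ECG, using the same five categories. Count a patient once per category, at the worst value. Use patients with at least one ECG in that category as the denominator.
2. In the existing threshold and findings tables, use patients with an ECG in the window as the denominator, and patients with any post-dose ECG for the pooled rows.
3. Add one row per dose group giving the number of patients with any ECG after the 60-minute one.
4. State that QTcF conclusions are limited to doses actually covered by an ECG.

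The cost is SAP wording and programming; dose times and ECG times are already collected, and no extra ECG is needed. The downsides are smaller high-dose cells, patients who appear in more than one dose category, and a dose to date that is partly confounded with time on treatment. The SAP should state the last two beside the new table.
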